#### **Recruitment for Formative Research:**

Inclusion criteria: We will include men and women who self-identify as black/African American (anywhere in the U.S.) with self-reported diagnosis of high blood pressure (systolic blood pressure of 120-159mmgHg or diastolic blood pressure of 80-99mmHg) whether or not they are taking medications.

Additional inclusion criteria: aged  $\geq$ 18 years; self-reported body mass index  $\geq$  18.5 kg/m2; has a smartphone with a data plan; has a working email address; and speaks English as primary language.

Exclusion criteria: We will exclude those participating in a related blood pressure/dietary trial; had cardiovascular disease event (e.g. stroke, myocardial infarction) in prior 6 months; active malignancy; recent psychiatric-related institutionalization; pregnancy – current or planned during the study period; and documented dementia.

#### RCT:

We will randomize 300 men and women with a:

- normal blood pressure (systolic BP of <120 mmHg or diastolic BP: <80 mmHg with diagnosis of hypertension) and/or taking blood pressure medications
- systolic BP of 120-159 mmHg or diastolic BP: 80-99mmHg whether or not they are taking medications
- If the BP is above 140 mmHg for systolic or 90mmHg for diastolic and not taking medications, we will refer them to their physician for follow-up.
- If the BP is ineligible (160+ mmHg systolic and/or 100+ mmHg diastolic) and is not taking medications, but states that they plan to start taking BP-lowering medications (per their PCP's recommendation/prescription) within the study recruitment period, they can be offered to reach out the study team via phone/email when their BP has stabilized. The same protocols will apply (confirming BP for eligibility) at the visit. If they are still ineligible due to high BP at that point, no other follow-up will occur and they will not be randomized.

Additional inclusion criteria: Aged  $\geq 18$  years; BMI  $\geq 18.5$  kg/m; has a smartphone with a data plan 2 and an email address; willing to receive daily text messages; willing and able to participate in 6 videoconferencing research visits over the 12 month period; speaks English as primary language; currently lives in the United States.

Additional exclusion criteria: not willing to update phone/device operating system; participating in another related clinical trial; cardiovascular disease event (e.g. stroke, myocardial infarction) in prior 6 months; active malignancy; recent psychiatric institutionalization; pregnancy—current or planned during the study period; documented dementia, lives in the same household as another participant already enrolled in Nourish (due to concerns about contamination if randomized to different arms), bariatric surgery in the last 12 months; currently on kidney dialysis; was told by healthcare provider to not eat a high-potassium diet; and/or investigator-discretion.

# **Subject Recruitment and Compensation**

#### **Formative Research Phase:**

Participants for DIP into DASH will be identified via passive recruitment strategies. These will include social media advertisements (e.g. NextDoor, Reddit, Facebook, Twitter, Instagram), and ResearchMatch, as well as working through community organizations that serve diverse populations, such as Piedmont Health, churches and other community organizations via their social media posts or flyers. We aim to recruit 50% men and 50% women. Participants who complete an interview will be compensated \$30 for their time. At the conclusion of the interview, participants will be asked if they would like to be contacted for the main RCT at a later date. If they say yes, they will be contacted by research staff and will follow all screening /consent procedures outlined for the main trial.

#### RCT:

Similar to the formative research, we will recruit participants using a multi-pronged strategy: 1) direct marketing; 2) local media; 3) social media; 4) community organizations; 5) primary care clinics; and 6) Duke MyChart recruitment messages will be sent to potentially-eligible participants using a computable phenotype based on our eligibility criteria within MyChart or email to patients without a MaestroCare account (see below). We have worked with the Maestro Care Optimization Team in DOCR and the Recruitment Innovation Center in the CTSI to ensure that both the computable phenotype and message are appropriate for our audience.

# Duke patients will be recruited as follows:

- 1) MyChart messages: We will utilize the MyChart research messaging platform by having the DOCR Maestro Care Research Analyst we have contracted with send the approved Nourish research message to potentially-eligible patients. The Analyst will run the phenotype through MyChart and include adult patients (18+ yo) located anywhere with an active MyChart account and a recent/upcoming appointment who have a diagnosis of hypertension, speak English, and who are not marked as deceased or have a diagnosis of dementia. The Analyst will send the approved message in batches and the message will refer interested patients to click on the study website to review the content, and fill out the online REDCap screener, consent and enrollment and/or contact the research team with questions.
- 2)MaestroCare outreach: Because demographic diversity is a critical part of this study, we do not want to exclude patients who may be eligible and interested in our study, but for whatever reason, have not activated a MyChart account. Thus, for Duke patients without an active MyChart account, the same eligibility criteria above will apply and will be part of the computable phenotype and criteria above. However, because there is no way to message Duke patients without an active MyChart account, when the messages are sent via MyChart to active patients, the Analyst will also send a

secure email with a spreadsheet with a list of potentially-eligible patients from the MyChart list and their contact information to the study coordinator. This will immediately be saved within the study's protected drive. Bcc'ed emails will be sent from the Duke email address using the approved email template to direct people to the study website for information and how to screen/consent and enroll, if interested.

We will also advertise the study using online flyers on websites including ClinicalTrials.gov, Duke Clinical Trials website, and ResearchMatch. We aim to recruit a sample that is at least 30% male and 40% racial /ethnic minority (similar to the demographics of Durham, N.C.). On a regular basis, we will assess the racial/ethic and gender of current participants so that we can do targeted recruitment, if necessary.

We will offer participants up to a total of \$160 in reimbursement via online Amazon gift cards, for the time spent taking surveys and participating in online research visits, over the duration of the study.

#### Risks/Benefits

#### **Formative Research:**

We anticipate minimal risk to the participant with the main risk being loss of confidentiality. The risk is detailed in the informed consent document for the participant. Risk will be minimized by assigning participants a study ID number that will be used on any forms in place of their name. Audio recordings will be captured with a recording via Duke Zoom or Duke WebEx on an encrypted computer and then immediately deleted from the computer once the audio files have been transferred to a Duke-provisioned Box account. All electronic files and the recordings will be securely stored behind the Duke firewall with access only granted to approved study staff. There is no direct benefit to the participant, but benefit to society may come from the study findings about how to approach hypertension treatment with a dietary approach and how to recruit more African American /black adults into clinical research trials.

**RCT:** Study personnel will not be responsible for the clinical care of participants and participants will be made aware of this delineation of responsibility. Participants will be referred to their primary care providers if any clinical problems are detected. Research assistants will be trained to detect clinical information that requires discussion with the PI and safety officer and that suggests referral to the provider. The informed consent will clearly describe all potential risks, including those specific to the use of the dietary tracking app. We anticipate minimal risk to the participant with the main risk being loss of confidentiality.

Potential benefits for study participants include improved diet quality, blood pressure and consequent reduction in cardiovascular risk. An additional benefit for some participants may be personal satisfaction in being part of a study that may have major public health implications for the community. No benefit from participation can be guaranteed. Potential benefits to others include the possibility that this research will help researchers evaluate the feasibility and efficacy of Nourish in promoting DASH dietary adherence. The minimal health risks to participants listed above are offset by the potential benefits to them and to society.

Disseminable interventions that promote improved diet quality and hypertension management in diverse communities can reduce the disproportionate impact of cardiovascular-related mortality and morbidity. This fully-powered 12-month randomized controlled trial aims to examine the efficacy of the Nourish intervention on changes in dietary quality and blood pressure among men and women with high blood pressure using the new blood pressure guidelines for nonpharmacological treatment. The findings from this study prepare us for a future pragmatic trial testing the implementation of Nourish in primary care. Our approach will also advance the science of digital health intervention dissemination. The minimal health risks to participants are offset by the potential benefits to them and to society, i.e., improved adherence to the DASH dietary appraoch and improved hypertension management, with consequent reductions in risk of comorbidities.

# **Data Analysis & Statistical Considerations**

#### **Formative Research:**

Interview audio recordings will be transcribed verbatim by Datagain Services. Study staff will conduct rapid analysis on transcribed interviews and/or use NVivo software to process the data with thematic analysis using a codebook derived from an initial coding of the same transcripts. After the codes are agreed upon and defined, all transcripts will be analyzed to identify common themes. Each transcript will be independently analyzed by two study staff members and consensus reached.

#### **RCT**:

Power and sample size. Using data from the pilot study we anticipate systolic blood pressure changes in intervention vs control as follows: -3.4 (SD=8.6) mmHg and 2 (SD=9.3) mmHg which results in an effect size of 0.6. The effect size for diastolic blood pressure is 0.75 based on changes in intervention vs control of -3.8 (SD=7.9) mmHg vs. 1.6 (SD=6.4) mmHg. With 90% power and a type I error rate (alpha) of .01, we can detect the expected effect size with the proposed sample size of 300.

Demographic and baseline data will be examined for integrity of randomization scheme and the homogeneity of study arms. If any demographic and baseline data are not balanced between the two study arms and are believed to affect the outcome, we will consider adjusting these variables in the modeling process. All analyses will be based on intention-to-treat (ITT) principles.

Aim 1: To understand how DASH score improves over time from baseline to 6 months and sustains through 12-month follow-up between study arms, we will plot observed DASH score vs. time (baseline, 1- month, 2-month, 4-month, 6-month, 12-month) by two study arms. Linear mixed models will be built to test the primary hypotheses. If we observe a linear trend in the previous plot, our model will contain fixed effects including group variable (intervention vs. control), time, and intervention by time interaction. To account for the correlations within the same participant over time, we include a random intercept and random slope for time in the model. If there is a quadratic trend in time, we will also include a quadratic term in time in the model. If any of the demographic or baseline variables are statistically different between the two study arms, then these variables will be included in a step-wise model selection process for the linear mixed model. We will estimate model parameters using the SAS/STAT procedure MIXED (SAS Version 9, Cary, NC). We will evaluate the primary hypotheses by testing the null hypothesis that the time by intervention parameter is 0.

Aims 2 and 3: Similar analysis will be conducted for changes in blood pressure (Aim 2) and relevant clinical, behavioral and psychosocial variables (Aim 3). If the distribution of any of the outcomes is heavily skewed, then we will either appropriately transform the data so it's normally distributed or use a generalized linear mixed model with an appropriate link function.

Missing data: Although we do not expect any missing baseline data, we anticipate no more than 20% missing values in longitudinal outcomes owing to dropout, missed completed dietary recalls, or missed follow-up assessments. In the pilot trial, we had 10% attrition with diet and blood pressure outcomes. Our primary model estimates intervention effects while accounting for missing data.

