# STUDY PROTOCOL

## Research Abstract

Over 100 million Americans suffer from high blood pressure and thus are at increased risk for cardiovascular disease and premature morality. Evidence supports the DASH (Dietary Approaches to Stop Hypertension) dietary pattern to reduce blood pressure. DASH is rich in fruits and vegetables, legumes, lean protein, and low-fat dairy, and reduced in red meats, sweets and processed foods. In the past 20 years, numerous trials have demonstrated the blood pressure-lowering effects of DASH across a diverse range of populations. As such, DASH is part of national dietary and blood pressure guidelines. Despite this strong evidence, fewer than 1% of U.S. adults with high blood pressure fully meet DASH guidelines. Like most efficacious interventions, the rate-limiting step involves dissemination. Behavioral trials testing DASH have been delivered primarily in-person, an approach that is effective but not accessible to the broader population. Innovative and accessible strategies to disseminate DASH, such as digital health, are critically needed. To address this need, we developed and tested the feasibility of a 3-month digital health intervention called DASH Cloud. The DASH Cloud intervention asked participants to track their diet daily using a commonly-used commercial tracking app with an extensive nutrient database. Our intervention technology platform extracted food and nutrient data from the app using an application programming interface (API). Each day, using this API software, we compared individual participant's nutrient intake to the recommended levels in the DASH diet. We then processed the data against an algorithm and sent automated text messages to each participant with information on DASH diet adherence and diet tips. Results indicated that we successfully recruited and retained individuals with elevated blood pressure, achieved high engagement with daily diet tracking and saw positive changes in diet quality. Based on the results of the feasibility trial, we will improve upon the personalization of the automated text messages and include a scalable and responsive way of delivering coaching, based on diet data received in the app. The efficacy of this approach will be tested via a fully-powered 12-month randomized controlled trial, Nourish. The trial will examine the effects of the intervention on changes in dietary quality and blood pressure among men and women with high blood pressure, using the new blood pressure guidelines for nonpharmacological treatment. The primary outcome is 6-month change in DASH adherence, as measured by 24-hour recalls. We will also measure DASH adherence at 12-months post-randomization. Secondary outcomes include changes in blood pressure and other physiological outcomes (e.g. weight, lipids, glucose). The scientific premise of this proposal represents establishing the efficacy of a previously deemed feasible approach for disseminating the DASH diet. With the millions of Americans in dire need of nonpharmacological treatments for blood pressure, the public health impact of disseminating the Nourish intervention could drastically reduce the incidence of cardiovascular disease. The findings from this study prepare us for a future implementation trial, testing the potential to implement DASH Cloud within clinics and other healthcare institutions, yielding

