Those eligible according to the screening questionnaire and who complete the baseline survey, will be invited to track their dietary intake on the NCI's ASA-24 tool for 2 unscheduled days. Once that is complete, they will be invited to participate in an online Duke Zoom Visit (Visit 1) and will be oriented to 1. 2. 3. 4. 5. the study, the Pattern Health dietary tracking app and taking blood pressure for the study via Zoom. They will be shipped a box of materials including an Omron digital blood pressure monitor. If they track their dietary data for a week, they will have their final eligibility assessed using home/self-monitored American Heart Association guidelines for blood pressure measurement while on the video Zoom call (Visit 2) with research staff. Once they attend Visit 2 and are deemed eligible based on their blood pressure being in range, participants will be randomized and oriented to their study arm.

Randomization will be 1:1 and conducted at the participant level using a permuted block randomization method and stratifying by blood pressure risk category, an important predictor of the intervention effect on blood pressure, and whether or not taking blood pressure medications. Blood pressure risk category is defined using the current American Heart Association guidelines, based on the average of the 3 readings:

Normal: If SBP < 80 mm Hg

Hypertension stage 1: SBP 130-139 mm Hg or DBP 80-89 mm Hg Hypertension stage 2: SBP 140-159 mm Hg or DBP 90-99 mm Hg

If average SBP is >160 mm Hg and/or DBP is >100 mm Hg, the participant will not be randomized at that time. Blood pressure will be taken again within the next 24 hours to determine final eligibility. If at the retake within 24 hours, the average BP it still above the range for study participation (160+ mm Hg for SBP and/or 100+ mm Hg DBP) and the participant is not currently on medications but plans on starting BP-lowering medications during the study enrollment period, they will told to reach out if they are interested in measuring their BP again once their BP has been stabilized by medications and appropriate follow-up from their PCP. All of the same data collection procedures will occur at that visit to take BP to assess final eligibility, prior to being randomized.

If the participant is on BP-lowering medications already and falls in the ineligible range as described above, they will be told they are ineligible for the study.

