## STATISTICAL ANALYSIS PLAN

We hypothesize that the intervention will lead to an increase in average DASH score of 2 units at 6 months and the control arm will achieve a 1-unit increase in DASH score. These estimates are based on the pilot study we conducted where both intervention and control arms achieved a 1-unit increase in DASH adherence from baseline to 3 months. Given the Nourish intervention is more intensive than what was delivered in the pilot, we anticipate a greater increase in DASH adherence. We estimate a standard deviation of 2 units for both intervention and control arms. This results in an effect size of 0.5, which is considered a medium effect size by Cohen's d. With 90% power and a type I error rate (alpha) of .01, a sample size of 242 will allow us to detect a difference of 1 unit in DASH adherence mean change score between study arms. We conservatively assume 20% attrition for this length of follow-up, resulting in the final analytic sample size of 300 total participants. With this sample size, we will also have power to examine intervention effects in systolic and diastolic blood pressure. Using data from the pilot study we anticipate systolic blood pressure changes in intervention vs control as follows: -3.4 (SD=8.6) mmHg and -2 (SD=9.3) mmHg respectively, which results in an effect size of 0.6. The effect size for diastolic blood pressure is 0.75 based on changes in intervention vs control of -3.8 (SD=7.9) mmHg vs. -1.6 (SD=6.4) mmHg, respectively. With 90% power and a type I error rate (alpha) of .01, we can detect the expected effect size with the proposed sample size of 300.

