## Statistical analysis plan

Demographic and baseline data will be examined for integrity of randomization scheme and the homogeneity of study arms. If any demographic and baseline data are not balanced between the two study arms and are believed to affect the outcome, we will consider adjusting these variables in the modeling process. All analyses will be based on intention-to-treat (ITT) principles.

We will assess the overall intervention effect on change of DASH score from baseline to 6 months by a two-sample t-test. To understand how DASH score improves over time from baseline to 6 months, and sustains through 12-month follow-up between study arms, we will plot observed DASH score vs. time (baseline, 2-month, 4- month, 6-month, 12-month) by two study arms. Linear mixed models will be built to test the primary hypotheses. If we observe a linear trend in the previous plot, our model will contain fixed effects including a group variable (intervention vs. control), time, and intervention by time interaction. To account for the correlations within the same participant over time, we will include a random intercept and random slope for time in the model. If there is a quadratic trend in time, we will also include a quadratic term for time in the model. To account for the stratified block randomization design, our models will also include our randomization stratification variables, blood pressure risk category and blood pressure medication status. If any other demographic or baseline variables are statistically different between the two study arms, then these variables will be included in a stepwise model selection process for the linear mixed model. We will evaluate the primary hypotheses by testing the null hypothesis that the time by intervention parameter is 0. Similar analysis will be conducted for changes in blood pressure and relevant clinical, behavioral and psychosocial variables. If the distribution of any of the outcomes is heavily skewed, then we will either appropriately transform the data so it's normally distributed or use a generalized linear mixed model with an appropriate link function.

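### Aim 2 plans a single blood-pressure effect and no estimate by pressure category, although the protocol says category predicts that effect; the pilot effect sizes are not shown to apply if people with normal pressure are randomised

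*Combined protocol and SAP*

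**What the plan says.** - **Analysis.** The protocol (Data Analysis & Statistical Considerations, RCT) tests the Aim 1 hypothesis with one time-by-intervention parameter and extends this to blood pressure: "Similar analysis will be conducted for changes in blood pressure (Aim 2) and relevant clinical, behavioral and psychosocial variables (Aim 3"). The SAP (Statistical analysis plan) repeats this and adds that "our models will also include our randomization stratification variables, blood pressure risk category and blood pressure medication status". Neither document states a category-by-intervention term or a category-specific estimate.
- **Role of category.** Design & Procedures describes the randomisation as "stratifying by blood pressure risk category, an important predictor of the intervention effect on blood pressure", together with medication status.
- **Who enters.** Subject Selection, RCT, lists as one entry route "normal blood pressure (systolic BP of <120 mmHg or diastolic BP: <80 mmHg with diagnosis of hypertension) and/or taking blood pressure medications", and Design & Procedures lists a normal stratum. The Remote Data Collection Protocol (blood pressure readings at Visit 2) instead requires average systolic 120-159 or diastolic 80-99 mmHg, or both, before randomisation. It gives no route for someone with both values below those ranges.
- **Source of the expected effect.** The effect sizes of 0.6 (systolic) and 0.75 (diastolic) come from the pilot. Of that pilot the Research Abstract says "we successfully recruited and retained individuals with elevated blood pressure". For a total of 300 the protocol then claims: "With 90% power and a type I error rate (alpha) of .01, we can detect the expected effect size with the proposed sample size of" that total.

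**The concern.** A variable said to predict the intervention effect is an effect modifier. Adding it as a main effect adjusts the level of blood pressure but forces the same treatment effect in every category. The plan therefore states that the effect varies and has no planned way of showing it.

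If people with normal pressure are randomised and respond less, the single Aim 2 estimate depends on how many of them enrol. A modest pooled result could then mean a weak intervention, or a useful one averaged with people who had little room to change. A category analysis chosen after seeing the data would be post hoc. The power statement has the same gap: it carries effect sizes from a pilot described as having elevated pressure into a sample that, on one reading of the eligibility text, is mixed.

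**Working it through.** **1. Inputs from the documents.** Protocol power paragraph: systolic change -3.4 (SD 8.6) against +2 (SD 9.3); diastolic -3.8 (SD 7.9) against +1.6 (SD 6.4); alpha .01. Allocation is 1:1, with 300 randomised. The SAP's 20% attrition leaves 300 × 0.8 = 240, or 120 per arm. Sidedness is not stated. A two-sided t-test is used because it reproduces the SAP's 242 for the DASH score (difference 1, SD 2, 90% power).

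**2. The plan's own figures.**
- Systolic: pooled SD = √((8.6² + 9.3²)/2) = 8.96; d = 5.4/8.96 = 0.60.
- Diastolic: pooled SD = √((7.9² + 6.4²)/2) = 7.19; d = 5.4/7.19 = 0.75.
- Systolic power (noncentral t): 98.0% with 240 analysed, 99.6% with 300.

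The claim of at least 90% power holds on these inputs, with slack, because the DASH score set the sample size.

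**3. Sign conflict.** The protocol gives -"3.4 (SD=8.6) mmHg and 2 (SD=9.3) mmHg which results in an effect size of 0.6"; the SAP gives -"3.4 (SD=8.6) mmHg and -2 (SD=9.3) mmHg respectively, which results in an effect size of 0.6". With the SAP's signs:
- Systolic difference 1.4 mmHg, d = 1.4/8.96 = 0.16, power 8.5% (240) or 10.9% (300).
- Diastolic difference 2.2 mmHg, d = 2.2/7.19 = 0.31, power 41% or 52%.

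Only the protocol's means yield the stated effect sizes, so steps 4 to 6 use them.

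**4. Dilution, if normal pressure is admitted.** The documents give neither the normal share p nor the relative effect f in that group. Both are assumptions here: p = 20-40%, f = 0 or 0.5, same SD throughout.

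Pooled effect = 5.4 × [(1 - p) + p·f], with 120 per arm and two-sided alpha .01. The raised-only column uses the raised-pressure participants alone at d = 0.60.

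| p | f = 0: mmHg (d), power | f = 0.5: mmHg (d), power | Raised only: per arm, power |
|---|---|---|---|
| 20% | 4.32 (0.48), 87.2% | 4.86 (0.54), 94.5% | 96, 94.1% |
| 30% | 3.78 (0.42), 74.9% | 4.59 (0.51), 91.4% | 84, 90.2% |
| 40% | 3.24 (0.36), 58.2% | 4.32 (0.48), 87.2% | 72, 84.1% |

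Power falls below 90% once p exceeds about 17% at f = 0, or about 34% at f = 0.5.

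**5. Precision by category.** 95% half-width = t × 8.96 × √(2/n per arm):
- Everyone (120): 2.3 mmHg.
- Raised at p = 30% (84): 2.7 mmHg.
- Normal at p = 30% (36): 4.2 mmHg; at p = 20% (24): 5.2 mmHg.

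**6. Interaction test.** Normal approximation, 0.6 against 0, 240 analysed: SE of the difference in d = √(4/(240p) + 4/(240(1 - p))). At p = 20% this is 0.323, giving power of 24% at alpha .01 and 46% at .05. At p = 40% it gives 38% and 62%.

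**The case against.** The strongest reply is that Aim 2 asks for the effect of the intervention against control among those randomised. A pooled intention-to-treat estimate adjusted for the stratification factors answers that question validly, and blood pressure is a secondary outcome. That stands, and it is why the pooled estimate should keep its place.

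Second, if the Visit 2 range is applied as written, nobody with both values normal is randomised and the dilution in step 4 does not arise. That also stands. What remains is that category is said to predict the effect and is not examined across the other strata.

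Third, the shares and relative effects are not in the documents, and the result turns on them. At f = 0.5 pooled power is slightly above raised-only power at every share shown, so pooling is not always the weaker choice.

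A reader might go further and infer that the 0.6 is wrong for the enrolled population, or that the trial is underpowered for blood pressure because of dilution. The documents do not support either. They give no pilot pressure range, baseline mean or medication mix, and no expected share with normal pressure. The most that can be said is that applicability is not shown. Nor do they rule out reporting by category; they are silent on it.

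**Conclusion.** The point holds in a limited form. By its own account the plan has an effect modifier for blood pressure, and it plans no estimate by category. That gap is worth closing whichever eligibility text applies.

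The loss of power is conditional on normal pressure being admitted, and on the assumed share and relative effect. On the protocol's inputs it runs from 98% undiluted down to 58% at the least favourable corner examined (40% normal, no effect there); with half the effect it stays at 87% or above. The sign conflict between protocol and SAP is a separate and larger threat to the Aim 2 power claim, and no restated figure is firm until it is settled.

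**What to change.** 1. Reconcile Subject Selection and Design & Procedures with the Visit 2 procedure on whether normal pressure is eligible. Define the categories so that they do not overlap. Subject Selection joins its normal limits with 'or', so 135/75 mmHg meets both the normal and the raised description. The normal cut-off printed in Design & Procedures also needs checking, although it may be damaged in the text read here.
2. Reconcile the control-arm signs in the two power paragraphs against the pilot data.
3. In the SAP, name the pooled intention-to-treat contrast as the result that governs Aim 2. Prespecify, as supportive, a randomised-category-by-intervention term for 6-month systolic and diastolic pressure, and report the effect with its confidence interval in each category.
4. In the power paragraph, say that the pilot effects assume raised pressure. If normal pressure is admitted, give power over a stated range of shares and relative effects, as in step 4 of the working.

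Cost: wording, plus model terms for a variable already collected for randomisation; no new data or visits. The downsides are wide intervals in a small normal category (about 4-5 mmHg half-width at 20-30% normal, against 2.3 overall), an interaction test too weak to settle much by its p-value, and a stated power that may look less favourable. Labelling the category results supportive avoids a second competing Aim 2 test.
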